#### **3.3.2 Number of Study Sites / Total Number of Subjects Projected**

The study will be conducted in at least 20 schools located in PA and NJ and include urban schools and suburban schools serving a diverse population. (It is possible that if a school drops out of the study that additional schools may need to be recruited to ensure that the study meets its enrollment goals. This would increase the number of schools to over 20

schools.) Schools will be randomly assigned to either OST-S or the control condition (TAU) (Refer to Section 8.1.1 for more details regarding participation).

The participants will include students in grades 3 thru 5 with organization, time management and planning (OTMP) skills deficits. We will enroll 3-4 students per grade level each year (3-4 students per group per school). Because we will hold 4 total groups at each school, the design targets, on average, 14 students per school over the course of the study. Therefore, we anticipate a total of 140 students from 10 schools in the OST-S group and 140 students from 10 schools in the TAU group. For every enrolled student, we anticipate one participating parent (280 parents). For every student, we will also enroll one participating teacher. It is possible that an individual teacher may participate with multiple students over the course of the study.

On average, participating schools include 3-4 classrooms per grade level. We plan to enroll students from two grade levels per school, although it is possible recruitment could include a third grade level. Additionally, there could be teacher turnover during the study, increasing the number of possible referring/participating teachers. Finally, because the 12-month follow up period will occur during the following school year for students in the study, an additional teacher will be enrolled for each student participant. Therefore, we estimate that up to 200 teachers will participate over the course of the study.

It is anticipated that we could enroll up to 40 additional school partners, with the expectation that we will have at least one school partner per school (20 total). We have projected the enrollment of 40 school partners to allow for potential school staff turnover within school buildings over the duration of the study.

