#### **Primary Objectives and Secondary Objectives Involving Academic Outcomes:**

As is customary, our estimates are in standard deviations (SDs; effect sizes). We examined power assuming 20 schools, inclusion of 3-4 students per grade level across two grade levels (3.5 students per school), and randomization at the school level. The design targets on average 14 students per school, or 280 total. To allow for 15% loss to follow up at the student level, we assume 120 students per arm. Each student will have data collected at 4 time points: baseline, post-treatment, 5-month follow-up, and 12-month follow-up. For analysis, we will use all available data until the time of dropout. For power calculations, we assumed conservatively a baseline measure and one follow up per student.

We accounted for the reality that longitudinal measures at the student level increase power and clustering of students within schools decreases power. We assumed three relatively modest correlations of outcome measures within student over time: 0.5, 0.6 and 0.7, which correspond to SDs of change of 1.0, 0.8, and 0.6 for a 1 SD cross sectional difference. Correlations of 0.5 lead to no increase in power from the design, and correlations of 0.6 and 0.7 correspond to approximately 10% and 20% increases in power. To account for clustering, we assumed intra-cluster correlations (ICC)=0.01, typical in school-based trials (Office of Behavioral and Social Sciences Research, NIH: <http://esourceresearch.org/tabcid/384/Default.aspx>). We also used ICC=0.038. This ICC value corresponds to variation across schools on the order of 0.4 SD of the distribution of outcome scores, or the equivalent to a range of means across schools of 1.6 SDs, a modest degree of inter-cluster variation. The design effects of these assumptions are 1.03 (small) and 1.11 (modest), to be expected with a relatively small number of students per school, and correspond to a reduction in the effective sample size of 3-11%.

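### Protocol section 6.1.4: design effects of 1.03 and 1.11 do not fit randomised schools of 12-14 students, and ICC 0.038 does not match a 0.4 SD spread between schools

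*Protocol*

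**What the plan says.** Protocol section 6.1.4 assumes 20 schools and describes the recruitment as "inclusion of 3-4 students per grade level across two grade levels (3.5 students per school), and randomization at the school level". It continues: "The design targets on average 14 students per school, or 280 total". On dropout: "To allow for 15% loss to follow up at the student level, we assume 120 students per arm". With 10 schools per arm, that is 12 evaluable students per school, and 12 is also the number per school in the power statement of the same section.

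Two ICCs are used, 0.01 and 0.038. Of the larger one the protocol says: "This ICC value corresponds to variation across schools on the order of 0.4 SD of the distribution of outcome scores". It then expresses the same spread in a second way, as a distance between the extreme schools: "or the equivalent to a range of means across schools of 1.6 SDs". On the cost of clustering it says: "The design effects of these assumptions are 1.03 (small) and 1.11 (modest"; these are said to "correspond to a reduction in the effective sample size of 3-11" per cent.

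Section 3.3.2 gives the group structure: "We will enroll 3-4 students per grade level each year (3-4 students per group per school". With four groups at each school, it arrives at 14 students per school on average. Section 8.1.1 has schools keep their assignment when they are recruited again in later years.

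Section 6.1.5 uses design effects twice more. Mediation power takes 1.1 for 220 students in 20 schools. Moderation power refers back to the range given in section 6.1.4.

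**The concern.** The design effect depends on how many students share a randomised unit. Here that unit is the school, and later cohorts from the same school join the same cluster. The printed design effects look too small for 12-14 students per school at the printed ICCs. The spread between schools looks too large for ICC 0.038.

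Section 6.1.4 is where the protocol justifies the cost of clustering, and a reader would take from it that clustering costs at most about a tenth of the sample. The section also leaves it unclear whether the ICC or the SD was the real planning input, and power depends strongly on which. The figures are used again in section 6.1.5. Section 6.2.2 says that any new power calculation will rest on the original assumptions.

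**Working it through.** **Inputs (protocol).** Randomisation by school, 10 schools per arm; 14 students per school enrolled; 120 per arm evaluable, so 120/10 = 12 per school; ICC 0.01 and 0.038; effect 0.5 SD (all section 6.1.4). Groups of 3-4 students, four per school (section 3.3.2).

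**1. Reproducing the printed design effects.** Formula: DE = 1 + (m - 1) x ICC, so m = 1 + (DE - 1)/ICC.
- 1.03 at ICC 0.01: m = 1 + 0.03/0.01 = 4.00.
- 1.11 at ICC 0.038: m = 1 + 0.11/0.038 = 3.89.
- Forward at m = 4: 1.030 and 1.114. DE - 1 is 3.0% and 11.4%, which matches the printed 3-11%. The loss proper, 1 - 1/DE, is 2.9% and 10.2%.
- At the printed 3.5 students: 1.025 and 1.095, so 3.5 does not give 1.11.
- 1.11 is also the value for m = 12 at ICC 0.01, but at m = 12 neither ICC gives 1.03.

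Of the cluster sizes tried (3.5, 4, 7, 12 and 14), only m = 4 returns both printed values.

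**2. Design effects for the randomised school.**

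| Students per school | ICC | DE | Loss, 1 - 1/DE |
|---|---|---|---|
| 12 | 0.01 | 1 + 11 x 0.01 = 1.110 | 9.9% |
| 12 | 0.038 | 1 + 11 x 0.038 = 1.418 | 29.5% |
| 14 | 0.01 | 1 + 13 x 0.01 = 1.130 | 11.5% |
| 14 | 0.038 | 1 + 13 x 0.038 = 1.494 | 33.1% |

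At ICC 0.038, 120 students per arm are worth 120/1.418 = 84.6, against 120/1.11 = 108.1 under the printed value.

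The 3.5 is a group size: 3.5 x 4 groups = 14 per school.

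**3. ICC and spread between schools.** Between-school SD = sqrt(ICC) in total-SD units.
- sqrt(0.038) = 0.195; a range of four SDs is 4 x 0.195 = 0.78. In within-school SD units, sqrt(0.038/0.962) = 0.199 and the range is 0.795.
- Printed: 0.4 and 1.6, about twice as large.
- Backwards: an SD of 0.4 needs ICC 0.4² = 0.16 (total-SD units) or 0.16/1.16 = 0.138 (within-school units).

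**4. Does the stated power survive?** SE = SD of change x sqrt(2 x DE/120); effect 0.5; two-sided alpha 0.05 (assumed, since section 6.1.4 gives none); noncentral t with 18 df (schools) or 238 df (students).

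The protocol lists SDs of change of 1.0, 0.8 and 0.6 for correlations 0.5, 0.6 and 0.7. These equal 2(1 - r), which is a variance. The SDs are 1.0, 0.894 and 0.775, so 0.775 is used for r = 0.7.

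| ICC (12 per school) | SD of change | Power, 18 df | Power, 238 df |
|---|---|---|---|
| 0.038 | 1.0 | 0.868 | 0.900 |
| 0.038 | 0.775 | 0.978 | 0.987 |
| 0.138 | 1.0 | 0.637 | 0.681 |
| 0.138 | 0.775 | 0.846 | 0.881 |
| 0.16 | 1.0 | 0.597 | 0.641 |
| 0.16 | 0.775 | 0.812 | 0.850 |

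The first row matches the protocol's 90% and above 0.85. With DE 1.114 in place of 1.418 and SD of change 1.0, power would be 0.934 (18 df) or 0.955 (238 df).

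**5. Mediation (section 6.1.5).** 220/20 = 11 per school. DE = 1 + 10 x 0.01 = 1.10 at ICC 0.01, and 1 + 10 x 0.038 = 1.38 at ICC 0.038. The stated 1.1 fits the smaller ICC only.

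**The case against.** The best defence is that the errors sit in descriptive text and not in the power run. At 12 per school, ICC 0.038, a design effect of 1.418 and an SD of change of 1.0, the calculation returns 0.90 and 0.87, in line with the stated 90% and above 0.85. That suggests the software was run with the school as the cluster. The SAP analysis uses no design effect at all: its mixed models carry random intercepts and slopes for school. This stands, with two limits. An SD of change of 1.0 belongs to a correlation of 0.5, whereas the protocol quotes 0.7, so the match is suggestive and not proof. It also takes ICC 0.038 as the true input.

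A second objection is that the cause is unknown. A cluster of four is consistent with one intervention group, but the documents do not say how 1.03 and 1.11 arose. This also stands: the mismatch is shown, its origin is not.

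On moderation, section 6.1.5 says that the simulations reflect clustering by school and that the design effect for an interaction tends to be well below that for a main effect. No loss of moderation power can therefore be asserted; only the inputs need confirming.

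A reader might infer that the trial was sized with groups as clusters and is underpowered for its main effect. The documents do not support that. Nor do they support the opposite, that main-effect power is unaffected whatever was meant: that holds only if ICC 0.038, and not 0.4 SD, was the planning value.

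**Conclusion.** Both errors hold. At school level the design effects are 1.11 and 1.42 (12 evaluable) or 1.13 and 1.49 (14 enrolled). The loss of effective sample is about 10% and 29%, or 12% and 33%, roughly three times what section 6.1.4 reports. ICC 0.038 and a 0.4 SD spread between schools cannot both be right.

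The consequence for main-effect power is conditional. Under ICC 0.038, the value named in the power statement, the stated power stands: 0.87-0.90 with an SD of change of 1.0 and about 0.98 with 0.775. Under 0.4 SD it would be about 0.60-0.68 and 0.81-0.88. These figures rest on equal schools of 12, two-sided alpha 0.05 and the standard design-effect formula. Severity: a minor correction to the sample-size text, with mediation and moderation inputs to confirm.

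**What to change.** 1. In section 6.1.4, replace the design effects by 1.11 and 1.42 at 12 per school (1.13 and 1.49 at 14 enrolled). Replace the loss by about 10% and 29% (about 12% and 33%), defined as 1 - 1/DE. Relabel the 3.5 students as per group, with four groups and 14 students per school.
2. Reconcile the ICC with the SD and say which was the input. If it was ICC 0.038, write about 0.2 SD and a range of about 0.8 SD, and keep the power statement. If it was 0.4 SD, give the matching ICC and restate the power.
3. In section 6.1.5, state that the mediation design effect of 1.1 corresponds to ICC 0.01 only (1.38 at ICC 0.038). Confirm the design-effect range used in the moderation simulations. Restate either power if it changes.

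Cost: a few numbers in the protocol text and one check of the simulation inputs. No extra participants and no change to the sample size.

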### 6.1.5 Secondary Objectives

**Mediation effects.** For this Aim, we rely on our own simulations as well as two programs in the R package. We assumed 220 evaluable students across 20 schools, and a design effect of 1.1. In brief, David Kenny's program "PowMedR" (Kenny 2016) suggests that power is adequate to detect an effect size of 0.3 SD for both the effect of treatment (A) on the mediator (M) and the effect of M given A on Y (conditional effect of OTMP on outcome). Likewise, the R package "medssp" (Vittinghoff 2015) suggests adequate power ( $> 0.8$ ) to detect effect sizes of 0.4 jointly and separately for both the association of A and M (effect of intervention on OTMP skills) and OTMP skills on academic performance (association of M and Y). Our own simulations, conducted using Stata v 14.1, to determine power to rule out a direct effect (of the intervention on outcomes not mediated by OTMP skills) suggest that only a large direct effect can be ruled out at conventional levels of statistical significance using the planned sample. 95% confidence intervals of results of all analyses will reflect post hoc power.

**Association between fidelity/engagement with OST-S, child clinical factors, and outcomes.** Descriptive and qualitative analyses will be used, so power calculations were not conducted.

**Moderation effects.** [name] to detect an interaction of treatment (A) and a modifier with 25% prevalence was estimated to be greater than 85% assuming a main effect of treatment of 0.5 SD and design effects from the clustering of students within school in the range noted previously noted, for an interaction effect of 0.67 SD. Owing to the absence of software for testing interaction effects, these estimates are based on our simulations conducted using Stata v 14.1. While these estimates continue to reflect the clustered (by school) design, the design effect in practice for the interaction of an across-cluster (intervention) and a within-cluster (student characteristic) variable tends to be much lower than for a main effect (intervention only). We choose a binary moderator for this calculation, and 25% prevalence, to be somewhat conservative. Prevalence of some moderators (e.g., inattention) are likely to approach 50%.

Descriptive methods will be used to examine costs and cost effectiveness. As such, power calculations were not conducted.

## 6.2 Preliminary Analysis to Respond to Project Officer

### 6.2.1 Goals of Preliminary Analyses

Our study team has identified three primary goals to address the question of whether OST-S is having its intended effect to address the request of the project officer. The goals of the preliminary analyses are contained within the original study aims and do not represent new aims.

1. **Determine whether OST-S may be effective in improving proximal outcomes (students' organization, time management, and planning [OTMP] skills) relative to a treatment as usual, waitlist control group (TAU-WL) at post-treatment.**

This goal is included within study Aim 1. We will examine only the primary study outcome, students' OTMP skills, assessed by parent and teacher ratings on the Children's Organizational Skills Scale (COSS-P, COSS-T), and we will examine outcomes only at post-treatment (not follow-up).

**2. Determine whether there may be a differential effect of OST-S on OTMP skills as a function of student grade level (3rd to 5th grade).**

This goal was included as an original study aim. It is especially important to examine this goal because there is good reason to believe 3rd graders may not respond as well to OST-S as older students. It is also important to examine this goal because by chance (due to randomization) the year impacted by COVID included mostly 4th and 5th graders, whereas the years before this included more younger students. Therefore, our sample of 175, which was designed to be evenly distributed across the grades, currently underrepresents 5th graders (Grade 3 –  $n = 64$ ; Grade 4 –  $n = 72$ ; Grade 5 –  $n = 39$ ).

**3. Determine whether there may be a differential effect of OST-S on OTMP skills as a function of the resource level of schools (low, middle, or high subsidized lunch rate).** This goal was included as an original study aim. It is important to examine this goal because prior research has suggested that schools with fewer resources (high subsidized lunch rates) might not do as well in implementing such interventions given the multiple stressors their staff face. That being said, fidelity implementation data suggests that our school partners generally are implementing the intervention with high quality regardless of school subsidized lunch rate.

### **6.2.2 Statistical Plan for Preliminary Analyses**

The study team, led by our statisticians, will compute descriptive statistics (mean, standard deviation, and 95% confidence interval) for change scores from baseline to post-treatment on the COSS-P and COSS-T in raw score format (mean item score). Descriptive statistics will be computed for each of the two arms of the study (OST-S, TAU-WL), as well as each grade-level subgroup (Grade 3, 4, 5) and school resource-level subgroup (low, middle, high subsidized lunch rate) within each arm. These descriptive statistics will be highly valuable in determining whether there is a signal of overall OST-S effectiveness, differential effects for grade-level subgroups, and differential effects for schools with low, middle, and high subsidized lunch rates. The study team will evaluate whether the lower limit of 95% confidence intervals is above 0, which would be suggestive of a significant difference. In addition, the difference in mean change scores between study conditions will be divided by the standard deviation of the control group (TAU-WL) standard deviation of change scores to provide a rough estimate of effect size for the entire sample, each grade-level subgroup, and each school subsidized lunch rate subgroup. Further, descriptive statistics will be computed to characterize the OST-S and TAU-WL conditions with regard to child sex, grade level, and school subsidized lunch rate subgroup.

In addition, we will determine whether there is a difference between intervention conditions with regard to the proportion of students who demonstrate a small, medium, and large degree of change in the expected direction from baseline to post-treat, as well as the proportion of students who demonstrate no change and change in the opposite direction. Degree of change on each measure (COSS-P and COSS-T) will be computed for each participant by subtracting baseline score from post-treatment score and dividing by the standard deviation of change scores for the condition to which the participant was assigned (OST-S vs. TAU-WL). Similar to guidelines established by Cohen (1988), effect sizes (ES) approximating .20 will be considered small; ES approximating .50 will be medium; and ES approximating .80 or higher will be large. We will conduct these analyses with all students in OST-S and TAU-WL as well as with subgroups based on grade level and subsidized lunch rate. **Because we did not include a plan to examine the proportion of students**

**responding to each condition in the original analytic plan, we are including a request for these analyses in this amendment.**

Descriptive statistics will be computed separately in three samples. First, using an intent-to-treat approach all enrolled participants will be examined. Second, using a per protocol approach most of the participants involved in the study during the COVID-19 shutdown in the spring, 2020 will be excluded from the sample. The only participants affected by COVID-19 who will be included are those for whom the duration of time between the collection of the COSS-P and/or COSS-T was  $\geq$  8 weeks (56 days) and the collection of post-treatment data for the COSS-P and/or COSS-T data occurred within 3 weeks (21 days) of the first date of shutdown (March 16). Third, using a per protocol approach two groups of participants will be excluded: (a) those participants affected by COVID-19 described earlier in this paragraph, and (b) those participants in the OST-S arm for whom COSS-T data were collected after the fourth intervention session (note: study team persisted with efforts to collect data in order to minimize missing data), because the initial sessions are believed to be critical for intervention success. **In our original statistical analysis plan, we planned to conduct intent-to-treat analyses, but we did not include a plan to conduct per protocol analyses. We are requesting an amendment to conduct per protocol analyses, as indicated.**

These exploratory descriptive analyses will be conducted on one occasion and a report will be sent to the IES project officer. By conducting the analyses in this way, our team is adhering to the approved IRB protocol. We will not conduct any statistical analyses in addition to those outlined above. To minimize bias in conducting these descriptive analyses, the deidentified data set needed for these analyses will be exported from REDCap by a study coordinator and will only include information about study arm (which will be deidentified), grade-level subgroup, school subsidized lunch subgroup, child sex, COSS-P and COSS-T raw scores at baseline and post-treatment, and sample subgroup (intent-to-treat, per protocol excluding most participants affected by COVID-19, and per protocol excluding most participants affected by COVID-19 and those in the OST-S condition with delayed collection of COSS-T data). A study statistician will conduct the analyses using the data set with deidentified study arms, and he will report findings to the study coordinator who will indicate the identity of the study arms for interpretation of findings.

If these exploratory analyses reveal there is a signal indicative of a main effect of intervention condition and/or an interactive effect of intervention condition and grade level and/or an interactive effect of intervention and school subsidized lunch rate subgroup, power calculations will be performed to determine the sample size needed to conduct tests of significance for the three study goals outlined above, which are the most important study aims. We will not perform power calculations again to conduct complex mediation analyses, which require a relatively large sample size. We will base power calculations on the same assumptions outlined in the original statical analysis plan, including an expected effect size of .50 and attrition of 15%.

This is a one-time request to provide summary statistics to the project officer for the purpose of obtaining a financial supplement. **If we obtain a supplement from the funding agency, we plan to submit another amendment to the IRB to clarify aims, update power calculations, and modify the statistical analyses plan.**

---

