## 5.2 Measures of Proximal Outcomes and Mediators – OTMP Skills and Student Academic Self-efficacy

Measures will be completed at baseline, post-treatment, and at 5-month and 12-month follow-up.

**Children's Organizational Skills Scale, Parent (COSS-P) and Teacher (COSS-T) Versions.** The COSS-P and COSS-T ([name] & [name], 2009) will be used to assess OTMP functioning at home and school. COSS total scores have good discriminant validity and are sensitive to treatment effects ([name] et al., 2013; Pfiffner et al., 2013). Each COSS version uses a 4-point rating scale (1=*Hardly ever or never* to 4=*Just about all of the time*). Although the COSS yields three subscale scores, only the total score will be used to reduce the number of measures in the analyses.

**Patterns of Adaptive Learning Scales – Academic Efficacy Subscale (PALS).** The 5-item Academic Efficacy subscale of the PALS (Midgley et al., 1998) will be used to evaluate students' perceptions of their competence in completing their classwork. Items are rated on a 5-item scale from 1 = not at all true to 5 = very true.

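### The only confidence-interval criterion in the preliminary analysis tests change within each arm, ignores school clustering and leaves its sign unstated

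*Protocol*

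**What the plan says.** Goal 1 of the preliminary analysis (Protocol 6.2.1) asks whether OST-S may improve OTMP skills relative to TAU-WL at post-treatment. Section 6.2.2 then sets out the following.

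- **Intervals.** The team will "compute descriptive statistics (mean, standard deviation, and 95% confidence interval) for change scores from baseline to post-treatment on the COSS-P and COSS-T". On the unit: "Descriptive statistics will be computed for each of the two arms of the study (OST-S, TAU-WL), as well as each grade-level subgroup". School lunch-rate subgroups within each arm are treated in the same way.
- **Criterion.** "The study team will evaluate whether the lower limit of 95% confidence intervals is above 0, which would be suggestive of a significant difference".
- **Between-arm quantities.** The difference in mean change is divided by the TAU-WL SD of change, overall and by subgroup. For degree of change, "we will determine whether there is a difference between intervention conditions with regard to the proportion of students" in each response category. Neither has an interval or a threshold.
- **Sign.** The order of subtraction is given only for the per-student degree of change, which is "computed for each participant by subtracting baseline score from post-treatment score" and then dividing by an SD. The change scores that carry the intervals have no stated sign.
- **Data.** The export is limited to a closed list of variables. Arm, grade, lunch-rate subgroup and sex are on it; a school identifier is not. No analyses beyond those listed are allowed.
- **Consequence.** "If these exploratory analyses reveal there is a signal indicative of a main effect of intervention condition", or of an interaction with grade or lunch rate, new power calculations follow. What counts as a signal is not defined.

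**The concern.** An interval for one arm's mean change that lies above 0 shows that the arm changed. It does not show that the arm changed more than the other. Students enter because teachers see them as struggling most (Protocol 3.4.5), so regression to the mean and ordinary maturation are to be expected in both arms. The criterion nevertheless reads such an interval as suggesting a significant difference.

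Two further gaps sit beside this. Schools were randomised and the main model has school random effects (Protocol 6.1.1), but section 6.2.2 makes no allowance for schools, and without a school code the statistician could not make one. The criterion is also directional, yet neither the sign of change nor the direction of benefit is stated.

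At stake is how a one-time report to the funder's project officer is read, and whether the team goes on to re-power the study and seek a supplement. The final efficacy test is not at stake.

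**Working it through.** The documents give no error rate, power or sample size for this rule, so there is no stated figure to reproduce. The checks below evaluate the rule as written.

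**Inputs.** Preliminary sample 64 + 72 + 39 = 175 (Protocol 6.2.1). ICC 0.01 and 0.038 (Protocol 6.1.4). *Assumed, not in the documents:* an even split, about 87 per arm; all 20 schools contributing, 175/20 = 8.75 students each; a common change of 0.2 to 0.4 SD of change; the ICCs applying to change scores.

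**1. Within-arm rule, improvement coded positive, no treatment effect.** Noncentrality = d × √87; the interval excludes 0 when t exceeds 1.988 (86 df). Students are taken as independent. The last column is p(1 − p), because the arms are independent.

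| Common improvement d (SD of change) | d × √87 | p: an arm's interval excludes 0 | OST-S excludes 0, TAU-WL does not |
|---|---|---|---|
| 0.2 | 1.87 | 45% | 25% |
| 0.3 | 2.80 | 79% | 17% |
| 0.4 | 3.73 | 96% | 4% |

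The intended rate for a lower limit above 0 is 2.5%.

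**2. The alternative sign.** Suppose change is post minus baseline and higher COSS is worse. Improvement is then negative and P(lower limit > 0) ≈ Φ(−d√87 − 1.96). At d = 0.2 this is Φ(−3.83), below 0.0001, so the rule would flag worsening and almost never improvement. The evidence on direction is indirect. "Each COSS version uses a 4-point rating scale" (Protocol 5.2), running from hardly ever to nearly always. Eligibility needs a rating of at least 3 on one of items 39–42, which record negative academic impact (3.4.5). The pilot reported benefit as a reduction in deficits (1.3). No section states the direction of the COSS total. Steps 1 and 2 cannot both apply.

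**3. Clustering.** Design effect = 1 + (8.75 − 1) × ICC. True error of a nominal 5% between-arm comparison that ignores schools = 2 × [1 − Φ(1.96/√DE)].

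- ICC 0.01: DE = 1.08, error 5.9%.
- ICC 0.038: DE = 1.29, error 8.5%.
- If fewer schools contribute, with 12 students each: DE = 1.11 and 1.42, error 6.3% and 10.0%.

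**4. Simulation with schools.** 20,000 runs, 10 schools per arm, 9 students per school, within-student correlation 0.6, ICC 0.038, improvement coded positive. Changes here are in cross-sectional SDs.

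| True change, OST-S / TAU-WL | OST-S lower limit > 0 | OST-S only > 0 | School-level between-arm 95% interval excludes 0 |
|---|---|---|---|
| 0 / 0 | 4.2% | 3.9% | 5.1% |
| 0.2 / 0.2 | 55% | 25% | 4.9% |
| 0.3 / 0.3 | 85% | 12% | 4.9% |
| 0.7 / 0.2 | 100% | 45% | 88% |

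The between-arm interval holds its error whatever the common change. In the last row, a true difference of 0.5 SD, the reading that OST-S alone must exceed 0 misses the effect in more than half of trials, because TAU-WL often exceeds 0 as well.

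**The case against.** The strongest reply is that section 6.2 is a one-time, exploratory, descriptive report and that the interval criterion is only part of it. The plan also gives a standardised between-arm difference and response proportions by arm. Any change to the analysis plan would need a supplement and a further IRB amendment, and the new power calculations use a fixed effect of 0.50, not the observed one. The main analysis (Protocol 6.1.1; SAP, Data Management and Analysis) compares arms and models schools. All of this stands. It limits the consequence but does not repair the criterion, which is the only place where section 6.2.2 attaches a meaning to an interval.

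Three stronger readings are tempting, and the documents do not support them.

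- *That the rule points the wrong way.* The order of subtraction is stated for a different quantity. The same paragraph speaks of change in the expected direction and uses positive cut-offs of .20, .50 and .80, which would fit improvement read as positive. What can be shown is that the sign is unspecified.
- *That the rule triggers re-powering.* The trigger is an undefined signal from the exploratory analyses as a whole.
- *That the preliminary analysis as a whole cannot show an OST-S effect.* The two between-arm descriptions could point to one; they simply carry no measure of uncertainty.

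A between-arm interval in mid-trial could also be said to resemble a formal interim look. The plan already reports the between-arm difference and both arms' means and SDs, so the interval reveals little more, but its status should be stated. Finally, about three schools per arm would fall in each lunch-rate stratum (10/3, if evenly split), too few for a reliable school variance by subgroup. The remedy should respect that.

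**Conclusion.** The concern holds in a limited form. The sole interval criterion is within-arm, takes no account of schools and has no stated sign; the signal that leads to new power calculations is undefined.

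If improvement is coded positive, equal improvement of 0.2 to 0.4 SD of change makes an arm's interval exclude 0 in 45% to 96% of trials without any treatment effect, and requiring OST-S alone to exclude 0 still gives about 25% at 0.2 SD and 17% at 0.3 SD. Under the other coding the rule almost never fires on improvement. The clustering part is modest: 5.9% to 8.5% instead of 5% at the protocol's own ICCs. The sizes rest on the assumed 87 per arm, 8.75 students per school and common change; the within-arm defect itself rests on none of them. It should be corrected, but it does not affect the validity of the final efficacy analysis.

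**What to change.** Amend section 6.2.2 as follows.

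1. Define the signal by the 95% interval for the OST-S minus TAU-WL difference in mean change, with a school random effect or a school-level analysis for the whole sample.
2. Report grade and lunch-rate subgroup differences with intervals as description only.
3. State how change is computed, which direction of the COSS total is worse, and hence which interval limit must clear 0. With post minus baseline and higher meaning worse, benefit would be an upper limit below 0.
4. Keep the within-arm intervals as description, with no reading of significance.
5. Add a deidentified school code to the export list.
6. State that this is a single descriptive look, with no efficacy claim and no stopping for efficacy.

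The cost is amendment wording and one export column; no new data are needed. Assuming 175 students in 20 schools, ICC 0.038 and 18 df, the overall interval would have a half-width of about 0.36, 0.32 or 0.28 SD for within-student correlations of 0.5, 0.6 or 0.7. Power for a true difference of 0.5 SD would be 0.79, 0.87 or 0.94, so the corrected criterion remains informative at this sample size.
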